## THE FOLLOWING INFORMATION MUST BE CMCVAMC-SPECIFIC, THAT IS, SPECIFIC TO WHAT WILL BE DONE WITH CMCVAMC-RECRUITED VETERANS.

H. Background and Significance: (Describe succinctly and clearly the past findings which justify the plan for this project. A summary of the relevant literature in the area of interest and reports of previous studies should be included.)

### Background

There is increasing concern about high unemployment and underemployment among the men and women who have served this country and the threat that the absence of gainful employment poses for the health, quality of life and economic security of veterans and their families.(13) The VA, the White House, and other public and private sector institutions have responded to this urgent crisis by committing time, energy and resources to help veterans and their spouses find adequate jobs.(14) Yet, while unemployment and underemployment are significant problems for far too many veterans, another group of veterans faces significant employment problems but receives little assistance. This is the large group of veterans who

are employed but, because of their depression, are encountering formidable obstacles to remaining engaged and productive in their work. Existing mental health and vocational services do not address this issue directly. The proposed study will test a new mental health/vocational intervention, the Veterans Work and Health Initiative (V-WHI), aimed at reducing the harmful impact of depression on veterans who are already in the labor market.

Depression is a highly prevalent, chronic and recurrent condition that frequently interferes with working. In the United States (US), depression is estimated to cost billions of dollars annually in lost work productivity principally as a result of job loss, premature retirement, work disability, at-work performance limitations (known as "presenteeism") and time lost from work (absenteeism).(6;7;15) The large cost of lost productivity is related both to the prevalence of depression in the working-age population (6.4% of employed US workers)(7) and the specific manner in which it interferes with working. Since Wells and colleagues(16) first reported on the disabling impact of depression in the 1980's, evidence of its human and economic burdens has continued to accumulate.(17-20)

A large study conducted by the Tufts research team screened 14,000 primary care patients, enrolling a sample of employed adults—286 of whom had depression and another 196 depression-free healthy controls. Subjects were observed for 18 months.(21;22) Though equivalent demographically and occupationally at baseline, depressed workers were found to be limited in their ability to perform basic job tasks at levels that were four times worse than the control groups' and they had triple the mean number absences. In addition, within six months after enrolling in the study, 15% of the depression group became unemployed; five times higher than the control group's job loss rate.(23) Moreover, the impact of depression on employment did not improve significantly over time.

The picture is bleaker for our newest veterans. In a recent study of employed OIF/OEF veterans seen in the Cpl. Michael J. Crescenz VAMC's Behavioral Health Lab (BHL) program, multiple dimensions of job performance were impaired by depression. Work limitations were responsible for average at-work productivity losses of between 9 and 10%; equivalent to the losses seen in civilian employed populations with moderate to severe major depressive disorder (MDD).(3)

Service Delivery Options. To our knowledge, there are no programs tailored specifically to employed veterans with depression who are having trouble at work. Various services exist that address facets of the problem, but care is fragmented and spread among a range of different programs, providers and sectors.

For example, within the Veterans Health Administration (VHA), physicians (psychiatrists and primary care providers) deliver the majority of the care that adults with depression receive. While there have been important gains such as improved access to higher quality diagnosis and treatment, especially in PACT or primary care settings, many physicians (already pressed for time) tend to focus on their patients' symptoms and treatment, not on their work problems. Ultimately, many physicians become involved in their patients' work problems around the time a disability claim is involved-which is sometimes too late to prevent it.

The VHA also has the largest and most comprehensive behavioral health services of any healthcare system. Behavioral health services are extensive but separate and include a range of acute inpatient, outpatient, emergency and consultation services, services and support for homeless veterans and intensive case management for veterans with severe mental illness (SMI). Included under behavioral health is the capacity for outpatient psychotherapy, but few psychotherapists are trained in addressing employment issues. Also within the behavioral health programs are comprehensive work training and supported employment services (e.g., for veterans with SMI). However, these do not target veterans who are gainfully employed. Vocational rehabilitation is available to veterans with a service-connected disability under the VetSuccess program (http://www.vba.va.gov/bln/vre/). Conceivably this program could help the portion of veterans with depression who have qualified for VA disability benefits and still

work. Additionally, an array of job training, placement and employment support services are available to veterans (and in some cases their spouses) through the White House Joining Forces Initiative(25) (which links to the federal OneStop Employment programs), the Wounded Warriors program and others. These programs are aimed at reducing the high unemployment rate(26) and underemployment among veterans and their families.

Finally, some adults with depression qualify for non-VA programs such as those offered in the workplace and/or the community. Many workers have access to Employee Assistance Programs (EAPs) through their employers, but seldom use them for depression assistance.(27) Community-based job training programs also could provide an option for some veterans. The Ticket to Work program is one example of an intervention to assist persons with disabilities with job preparation and job placement. Historically, this program rarely has been involved with helping people who are already employed. State and federal vocational rehabilitation programs also provide employment support to persons with disabilities but their services are available mainly to adults with the most severe health problems, most of whom have little or no work experience. Insurance programs, such as the US Social Security disability programs and private disability carriers, provide income replacement. Finally, The Americans with Disabilities Act(28), while potentially helping with job accommodations, has generally helped more with hiring than retention.

Taken as a whole, the V-WHI has the potential to fill a void in existing services while offering a paradigm shift for traditional mental health services from its historical focus on symptom-based pathology to a new emphasis on recovery, rehabilitation and functioning. This shift is consistent with the emerging policies from the Office of Mental Health Services and veterans' preferences. If successful, the V-WHI could be offered both to veterans in VHA care and the large group of veterans who are eligible for services but choose to access care outside of the VA system.

### Significance of the Research

Employed veterans with depression are vulnerable to a wide range of employment problems but a gap in their care still exists. Typically, health and work problems are addressed in separate silos and even systems. And, many interventions are geared for populations with work problems that are less intense (depressed with no work problems) or more intense (veterans with SMI).

Moreover, research has been surprisingly limited in its conceptualization of the mechanisms linking depression to poor work outcomes. Almost completely missing is a discussion of functional performance. Over a decade of research, the Tufts team has established that depression is related to a range of functional difficulties and these lead to worse employment and economic outcomes.

New care models that integrate psychological and work-focused interventions to achieve functional improvements may offer a solution. This study will test a new multi-modal care program that is aimed at filling the gap. It will test whether the V-WHI will be effective in helping veterans to function effectively and productively at work. It is the first program to integrate mental health and vocational care for working veterans with depression who are already employed. If the V-WHI is effective, the proposed research will make a significant contribution to the science of functional improvement and work disability prevention. Eventually, this program could have a major impact on the health, quality of life and economic security of veterans and their families and save the VA and the nation millions of dollars in lost productivity.

### **Preliminary Studies**

Preliminary Research Related to V-WHI Program Development. As discussed above, despite the secondary work benefits of high-quality treatment, research has shown that it is not enough to overcome the significant work disruption that depression often causes. Taking cues from the care of problems such as musculoskeletal pain, in which return to effective functioning is regarded as an important goal, the Tufts research team concluded that employees with depression may also benefit from work-focused care addressing the medical, psychosocial and vocational dimensions of functioning. Prior research by the Tufts team and others has suggested several strategies.(29) For instance, studies of collaborative care for depression(30-35) have shown that patient clinical outcomes are better when care is organized to support provider-patient teams with care manager involvement.(33;36) Similarly, occupational medicine and disability research has shown that work-injury or disability claimants return to work more quickly when medical providers, workplace managers, and the employee collaborate.(29;37) These results imply that coordinated care involving mental health care providers, the employee, and other professionals familiar with the work situation may bridge the gap between the medical and work domains. In addition, an extensive literature demonstrates the effectiveness of cognitive-behavioral therapy (CBT) in improving mental health and functioning. CBT is also flexible and can be provided as a brief intervention through in-person, telephonic, (38-40) or electronic modalities. (41-45) Finally, studies of supported employment for severely and chronically adults with mental illness and other persons with disabilities offer insights into the importance of achieving a "fit" between the person and the work environment. Methods of enhancing this fit have included job coaching, providing social supports, and/or instituting modifications at work (e.g., flexible scheduling).(9;10)

V-WHI Work Coaching and Modification Component. The aim is to identify specific job performance difficulties related to depression and guide the veteran towards changing modifiable aspects of his or her work methods and/or work conditions. Conceptually, it draws upon principles articulated in research on return to work programs for work-injured employees and work disability claimants,(46) employment support for severely and chronically mentally ill populations(9;10;47;48) and disability theory(49) which consider social role performance to result from a complex person and environmental interaction.(10;50) In this WHI component, the counselor focuses initially on obtaining an accurate assessment of the participant's job and work limitations using both the WLQ and probing techniques. The counselor then elicits information from the participant regarding individual and environmental barriers that may be interfering with effective functioning. This step is followed by efforts to guide the participant towards initiating changes aimed at improving functioning. The recommended changes are designed to be normative and safe but do not involve formal job accommodations. The recommended approaches are behavioral and/or environmental depending on the nature of the problem and the person's preferences. For example, a veteran may be having difficulty working because he feels disorganized and/or distracted. After careful assessment of his work limitations, work conditions (demands, control, supports and environmental factors) and preferences, the V-WHI counselor may suggest strategies such as using organizing tools, asking coworkers for feedback and advice and/or periodically turning off email and telephones. If disorganization and/or distraction are related to cognitive/emotional issues such as ruminating and wandering thoughts, the counselor may suggest a CBT strategy.

Work-Focused Cognitive Behavioral Therapy (CBT) Component. Depression is associated with maladaptive cognitions behaviors and interpersonal functioning that may interfere with work functioning. Thus, individuals with the disorder will, conceivably, benefit from developing a new repertoire of more adaptive behavioral and cognitive strategies and coping skills. The WHI incorporates CBT strategies originally developed by Beck;(51-53) Lewinsohn and Antonuccio, Steinmetz and Teri;(54) and adapted by others.(38-40;42-45;55) CBT

### R&D Service (151)

involves identifying and changing negative cognitions (e.g., negative self-talk, cognitive distortions, negative patterns of attribution) and maladaptive behaviors (e.g., avoidance, procrastination) that contribute to functional limitations. Studies report that CBT is an effective, time-limited alternative to more traditional therapeutic approaches to depression treatment,(56) and that it improves patients' symptoms and functional outcomes.(18;57) Treatment trials of enhanced primary care have shown that CBT interventions reduce social role disability.(43;58-61) CBT has also been studied within employee populations showing moderate positive effects on mental health, quality of working life, and absenteeism.(24;62-65) Recent studies using telephone-based CBT strategies have demonstrated efficacy.(66-68) These strategies are educational, goal-oriented, and time-limited collaborative endeavors that attempt to help individuals learn skills that enable more adaptive coping and functioning. The V-WHI is based on similar CBT approaches and is supported by a manual, named Creating a Balance.(69) Prior studies using telephonic CBT and Creating a Balance have demonstrated emonstrated improvements in depressive symptomatology. The V-WHI has adapted Creating a Balance to emphasize the program's work focus.

WHI Tests. Two studies of the WHI have been completed to date and a third national study will be completed in 2013. The WHI studies were sponsored by the CDC (R01 DP000101), NIMH (R34 MH072735) and the NIA (R01 AG 033125-01A1), respectively.

The first WHI pilot test was conducted in a national aeronautics manufacturing firm. It used a quasi-experimental, pretest-posttest design with an external comparator. In that initial study, employees in the WHI program had statistically significant improvements in at-work performance and productivity based on the WLQ (described below).(8)

The second study was an RCT comparing the WHI to usual care for depression conducted in Maine State Government; Maine's largest employer. The RCT enrolled 59 employees in the WHI group and 27 non-depressed controls. Employees with other major psychiatric or physical co-morbidities were excluded. The groups were equivalent at baseline demographically, clinically and occupationally. As in the proposed study, the Maine study's primary endpoints were the WLQ at-work performance and productivity scores and healthrelated work absences and productivity loss based on the WLQ Time Loss Module. PHQ-9 depression severity was also assessed. The results were impressive. Although there were no baseline differences between the WHI treatment group and the usual care group ( $p \ge 0.05$ ), by follow-up the WHI treatment group had significantly better scores on every outcome and differences in the longitudinal changes were all statistically significant (p= 0.027 to 0.000). The new program was superior to usual care and resulted in an estimated annualized productivity cost savings of \$6000 per participant.

The third and ongoing study of the WHI is an RCT testing its effectiveness and economic impact for middle-aged and older workers with depression. The study includes 23 employers and organizations (e.g., AARP). WHI care is provided by OptumHealth EAP counselors, under the supervision of the Tufts team. This complex field trial will end enrollment in 2012. It has enrolled over 410 employed adults with depression. As seen in the two prior trials, the burden of depression is large. The frequency of work limitations is indicated by the WLQ scale scores.

Each WLQ score indicates the mean percentage of time in the 2 weeks prior to baseline that health problems limited ability to perform each category of work tasks: time management, physical tasks, mental and interpersonal tasks and output tasks (related to quality, quantity and timeliness of work). For example, among employees with mild depression symptom severity, work limitation scores range from being limited 19% of the time to 28% of the time. For those with moderate symptom severity, the range is 20% of the time to 42% of the time. For employees with severe symptoms, limitations range in frequency from 32% of the time to 61% of the time. The associated at-work productivity loss was between 7 to 14% on average in the three respective severity groups. Mean absences due to health or medical care in the prior two weeks ranged from just under 1 day to 2.4 days. Missed days translate into productivity losses between 7% and 22%. The burden of depression is also reflected by diagnosis. Functioning is poorest in the double depression group. Finally, the number of co-morbid conditions, which in this study are primarily physical, was important only for performance of physical job tasks.

- I. Purpose of the Project: (Clearly provide the purpose of this research project.) This study's goal is to enable employed veterans with a depression disorder to remain functionally independent and participate fully in the labor market. Its Aim 1 objective is to test the effectiveness of an innovative telephonic counseling program for employed veterans with depression, the Veterans Work and Health Initiative (V-WHI), which uses both psychological and vocational interventions. The Aim 2 objective, which is contingent on the effectiveness of the V-WHI, is to quantify its return on investment (ROI). This study will have three sites: the Cpl. Michael J. Crescenz VAMC, theVA, and the VA TVHS. The Coatesville VAMC was closed as a study site in August 2016, and further references to the closed site no longer appear in the protocol summary.
- J. Describe the Research Questions or Hypotheses (that is, what questions are you trying to address by conducting the research.) The effectiveness of the V-WHI approach will be tested in the context of a randomized controlled trial (RCT). The following hypothesis will be tested: veterans receiving V-WHI will have better work outcomes at time 1 (T1) than the usual care group (BHL only) as measured by at-work productivity loss known as presenteeism. A sub-hypothesis for Aim 1 is that the V-WHI effect at T1 will be sustained at least until the final follow-up (T2). Secondary T1 outcome measures expected to improve include absenteeism, depression symptoms and health-related quality of life (HRQOL). Hypothesis 2 is that the return on investment (ROI in the V-WHI at time T1 will be positive, exceeding 1). Analysis of ROI will be contingent upon confirmation of Hypothesis 1. ROI will be estimated based on the marginal group difference in productivity (presenteeism and absenteeism combined) relative to the marginal V-WHI program costs.
- K. Primary Outcome Variable(s): (Define the primary outcome variable(s) used to support the study objectives (e.g. if the objective is to show that treatment A is superior to treatment B in the treatment of subjects with essential hypertension, the primary outcome variable is blood pressure measurement.) The main variables for outcomes analysis quantify health-related decrements in work performance and productivity (presenteeism). In addition, we will assess work loss and work retention based on employment status and other work outcomes such as weekly hours. To help us interpret the scores, we have extensive comparative data from clinic and population-based samples for the Work Limitations Questionnaire (WLQ), the WLQ Time Loss Absence Module,(11;12) and other employment status items (e.g., job loss).
- L. Secondary Outcome Variable(s): (Define the secondary outcome variables. Such measured variables should also include the timing of measurement.) The study will also measure secondary outcomes related to work including work absences related to health and/or treatment, depressive symptoms and health-related quality of life (HRQOL). Additional study endpoints will include loss of employment vs. retention of employment, new disability claims and change in job hours. While relevant, they occur infrequently. Depression symptom severity is measured with the PHQ-9. The HRQOL is measured with the VR-12 which generates a physical component score and a mental component score.

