**Power Analysis and Sample Size** 

In this study, we wish to power the study to obtain an effect size that represents a minimally clinically important difference on the health outcomes and an economically important difference related to work productivity impact (the primary endpoint). Currently, MCID is established for the PHQ-9(2) and the PCS and MCS for the VR-12.

For the PHQ-9, we anticipate that the average subject will have an average baseline score of 15 on a 0-27 scale. A clinically-meaningful reduction of 5 points, which is stated in the literature, would have 100% power to be detected. For PCS and MCS, a clinically-meaningful 5-point improvement would afford 99% power.

With regard to Hypothesis 2, corresponding to the study's power to detect an economically important difference, the primary criterion is whether an ROI greater than 1 can be obtained. This analysis is described in the following section.

For presenteeism, a reduction of 1.2% in productivity loss (or a relative improvement of 1.2%) would have comparable value to the maximum expected cost of treatment, meaning that the economic value of treatment would exceed the cost. A sample size of 100 treatment and 100 controls after subject dropout would achieve an 83% power for this outcome. To be sure of getting these numbers based on previous success rates, we will recruit 250 subjects prior to 50-50 randomization within full time and part time strata.

4.2. Define plans for data and statistical analysis, including key elements of the statistical plan, stopping rules and endpoints.

In this section, we describe the methods for testing hypothesis 1, several additional analyses including testing related to the secondary study outcomes and sensitivity testing related to both the primary and secondary study endpoints and statistical power calculations. Following this section, there is a description of the methods for testing hypothesis 2, which consists of the ROI analysis.

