### Aim1. Hypothesis 1.

The primary hypothesis of the study is that presenteeism, measured by the WLQ productivity loss score (PL), will be lower in the first (T1) follow-up for the V-WHI treatment compared with IC only. Productivity loss is computed using data

from the WLQ's four work limitation scales and then applying an empiricallybased algorithm to the scale scores. Details of the study on which the scoring methodology was based are included in Lerner et al, 2003.(12)

For hypothesis 1, the null hypothesis that the two groups are equal. The null hypothesis is tested by fitting the ANCOVA equation:

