## PL1 = b\*PL0 + g\*X + c\*I(V-WHI) + error

where PL0 refers to the baseline WLQ productivity loss and PL1 refers to the post-treatment WLQ productivity loss, X represents a set of covariates such as full-time or part-time stratum assignment, age, gender, baseline depressive symptom severity and, prior depression, and, g represents their regression coefficients, and I(V-WHI) indicates that the veteran is assigned the experimental treatment. The regression coefficient c will be tested by a t-test at 5% significance level of c=0 vs. the alternative c $\Box$ 0. Although we believe that c<0 (the treatment reduces presenteeism) we test against inequality because a two-sided test is conservative and conventional.

The primary analysis is "intent to treat" that is, all persons assigned to each group will be followed up to the maximum possible extent, even if they drop out of IC or V-WHI treatment, and analyzed as a part of their assignment group.

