A third sensitivity issue is related to the relationship of T1 and T2 outcomes and ways they might be characterized. For these purposes, we would analyze T2-T1 outcomes to state how well the results were maintained, or analyze all measurements jointly using mixed models where there are random effects due to subject, e.g.,

PLit= g\*X + g1\*X\*T1 + g2\*X\*T2 + a1\*T1 + a2\*T2 + c1\*T1\* I(V-WHI) + c2\*T2\* I(V-WHI) + ei + eit

where the subscript t refers to the time, 0, 1 or 2, and T1 and T2 are indicator variables corresponding to T1 and T2.

Hypothesis 2. Cost Benefit Analysis/ROI Determination.

We will analyze the ROI of the experimental program if Hypothesis 1 is confirmed and test whether, consistent with Hypothesis 2, the ROI to achieve productivity gain is greater than 1. The general approach will be to compute the cost and benefit components of the ROI. The ROI is computed as the incremental cost minus the incremental monetized benefit divided by incremental cost (amount invested in the new program). A ratio exceeding one indicates a favorable ROI. Our Hypothesis 2 analysis will consider only that portion of the intervention's incremental cost related to the V-WHI and will quantify incremental benefit as the monetized value of productivity improvements. We will not consider consumption of resources not directly related to depression because of the complexity and scope of that type of analysis in this population. Nor will we include subject costs and benefits. Subjects presumably engage in the intervention because the resulting additional functional effectiveness and well-being outweigh their incurred costs (e.g., the time consumed). While we could measure the costs incurred by veterans in the program, we cannot measure the corresponding functional benefits in their personal lives.

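### The ROI estimate itself, not only the test of Hypothesis 2, is withheld unless presenteeism at T1 is significant, although ROI also counts absenteeism

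*Combined protocol and SAP*

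**What the plan says.** Aim 2 is made conditional in three places, consistently:

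- Section I (Purpose): "The Aim 2 objective, which is contingent on the effectiveness of the V-WHI, is to quantify its return on investment (ROI".
- Section J (Hypotheses): "Analysis of ROI will be contingent upon confirmation of Hypothesis 1".
- Section W.4.2, Hypothesis 2: "We will analyze the ROI of the experimental program if Hypothesis 1 is confirmed".

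The condition is a single test on a single outcome. W.4.2, Hypothesis 1, reads: "The primary hypothesis of the study is that presenteeism, measured by the WLQ productivity loss score (PL), will be lower in the first (T1) follow-up". On the ANCOVA treatment coefficient, W.4.2 states that "The regression coefficient c will be tested by a t-test at 5% significance level", and "we test against inequality because a two-sided test is conservative and conventional".

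The ROI benefit is wider than that outcome. Section J: "ROI will be estimated based on the marginal group difference in productivity (presenteeism and absenteeism combined". The Benefits paragraph of W.4.2 adds the reduction in the proportion of time absent to the reduction in presenteeism loss, then multiplies the sum by work hours and the median loaded wage. One point of absence therefore counts as much as one point of presenteeism.

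W.4.1 says of a 1.2-point reduction in presenteeism loss that it "would have comparable value to the maximum expected cost of treatment", and gives 83% power for it with 100 per arm after dropout.

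The Secondary Analyses part of W.4.2 lists absenteeism and combined productivity loss as secondary outcomes, with no condition attached.

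**The concern.** Putting a confirmatory test of Hypothesis 2 behind Hypothesis 1 is ordinary hierarchical testing. The plan goes further. Section I describes Aim 2 as quantifying ROI, and the whole quantification is dropped if Hypothesis 1 is not confirmed. No section provides an ROI estimate in that case.

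Two consequences follow. First, a non-significant presenteeism result is not evidence that benefit falls short of cost, and absenteeism plays no part in the condition. Absenteeism is not a minor component: Section H reports absence-related losses of 7% to 22% in an earlier WHI study, against 7% to 14% for presenteeism, and Section J expects absenteeism to improve. A program with a favorable combined benefit could end the trial with no ROI. Second, when ROI is reported, its presenteeism component comes from trials selected for a large enough presenteeism estimate, so on average it leans upward.

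At stake is whether the VA receives a cost-benefit estimate at all, although earnings, absence, utilization and counselor-time data are collected whatever Hypothesis 1 shows.

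**Working it through.** **Inputs from the documents.** Effect 1.2 points, 100 per arm, power 83% (W.4.1); two-sided alpha 5% (W.4.2); 250 randomized at the main site, with 225 expected at T1 and 200 at T2 (M.2.2); 100 more randomized at the second site (R.1). No SD is given.

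**Step 1. The plan's own figure.** Without an SD, 83% cannot be reproduced independently. It can be inverted. Power of 83% needs effect/SE = 1.960 + 0.954 = 2.914, so SE = 1.2/2.914 = 0.412 and SD = 0.412/√(2/100) = 2.91. The recruitment figure does reproduce: 200/(1 − 0.20) = 250.

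**Step 2. Chance of no ROI at the design effect.** This is 1 − power = 1 − 0.83 = 17%, with no SD needed. The 100 per arm behind the 83% matches the number expected at T2, but Hypothesis 1 is tested at T1, so two other sample sizes matter:

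- main site at T1: 225/2 = 112.5 per arm;
- both sites pooled, assuming the same 10% loss at the second site: 350 × 0.90 = 315, or 157.5 per arm.

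**Step 3. Average inflation when the condition is met.** With true effect d, P(pass) = Φ(d/SE − 1.96), and the mean passing estimate is d + SE × φ(1.96 − d/SE)/P(pass). For d = 1.2 and SD 2.91:

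| n per arm | SE | Smallest passing estimate | P(no ROI) | Mean passing estimate | Average inflation |
|---|---|---|---|---|---|
| 100 | 0.412 | 0.81 | 17% | 1.33 | 10% |
| 112.5 | 0.388 | 0.76 | 13% | 1.29 | 8% |
| 157.5 | 0.328 | 0.64 | 4.5% | 1.23 | 3% |

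**Step 4. Other true presenteeism effects.** These are assumptions, not figures from the plan. With 100 per arm:

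- 0.6 points: no ROI 69%, inflation 79%;
- 0.9 points: no ROI 41%, inflation 30%;
- 1.8 points: no ROI under 1%, inflation 0.5%.

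**Step 5. Benefit partly through absence.** Suppose the 1.2 points arise as 0.6 from presenteeism and 0.6 from absence. The monetized benefit is the same as for 1.2 points of presenteeism, yet the chance of no ROI is 69% (66% with 112.5 per arm, 55% with 157.5). With 0.6 plus 1.8 points, benefit is twice the cost (2.4/1.2) and the chance is unchanged, because absence does not enter the condition.

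**Step 6. Sensitivity to the SD.** At 1.2 points and 100 per arm, the chance of no ROI is 8% for SD 2.5, 19% for SD 3.0, 32% for SD 3.5 and 44% for SD 4.0.

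**The case against.** The strongest reply is that the condition is deliberate. Section I poses Aim 2 only if the program is effective, the rule is stated openly and identically three times, and it is a pre-specified hierarchy. That stands, and it justifies conditioning the claim. It does not justify withholding the estimate, since an interval reported without a claim costs nothing in error control.

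A reader might infer that an absence-driven benefit would go unseen. The documents do not support that: absenteeism and combined productivity loss are analyzed as secondary outcomes regardless. Only the comparison with cost is lost. The exploratory analysis at the end of W.4.2 does not restore it, because it is additional to testing Hypothesis 2 and is only to be considered.

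A reader might also infer that every reported ROI is inflated. It is not. At 1.2 points with 100 per arm, (0.83 − 0.50)/0.83, or about 40%, of passing estimates lie below the true effect. Nor does the condition create favorable results: every estimate above 1.2 passes anyway, so the condition only removes low estimates from those reported.

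Three limits on the arithmetic also stand. The ROI input is described as average change by group, not the ANCOVA coefficient, so selection carries over through correlation and the percentages describe the tested coefficient. Absenteeism is inflated only as far as its estimate correlates with presenteeism, which the documents do not quantify. And W.4.2 defines ROI as cost minus benefit over cost, whose sign does not fit a favorable value above one. If it was meant as benefit minus cost over cost, exceeding one takes about 2.4 points combined; were those all presenteeism, the condition would almost never block.

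**Conclusion.** The point holds as one about withholding an estimate. The plan makes reporting of ROI depend on significance of one of its two benefit components. At the effect it equates with maximum treatment cost, the chance of no ROI is 17% on its own power statement, about 13% at the T1 number expected at the main site, and about 4.5% if the sites are pooled. It rises well above that if part of the benefit comes through absence.

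The selection effect is secondary: about 10%, 8% and 3% on average at 1.2 points, more at smaller true effects, negligible near 1.8. Everything except the 17% rests on the back-solved SD of about 2.9; a larger SD worsens both problems. The pooled figures further assume a joint analysis with 10% loss at both sites.

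It would be too strong to say that the trial gives no answer about combined benefit, or that any ROI it reports must be too high. The primary analysis is unaffected. This is a low-cost improvement worth making.

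**What to change.** Reword Section I, Section J and the Hypothesis 2 text in W.4.2 so that ROI is estimated whatever the result of Hypothesis 1 and reported with a bootstrap 95% confidence interval. Keep the formal claim that ROI is greater than 1 behind confirmation of Hypothesis 1. If Hypothesis 1 is not confirmed, present the ROI as an estimate with its interval and no claim.

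Reporting ROI unconditionally removes both the chance of no estimate due to this condition and the selection in the reported estimates. ROIs that are formally claimed remain selected, which the report can say.

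The cost is a wording change and one analysis on data already being collected, with no added participants or visits. The downside is that an imprecise or unfavorable ROI may have to be reported after a null primary result.
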